## NOTES:

- If the study treatment stop date is missing, then the AE will be considered to be On-Treatment.
- Please refer to Appendix 5: Reporting Standards for Missing Data for handling of missing and partial dates for adverse events. Use the rules in this table if the adverse event onset date is completely missing.

#### 10.3. Appendix 3: Data Display Standards & Handling Conventions

#### 10.3.1. **Reporting Process**

Software						
The currently supported versions of SAS software (9.4 or higher) will be used.						
Reporting Area	Reporting Area					
HARP Server	Not applicable					
HARP Compound Not applicable						
Analysis Datasets						

- Analysis datasets will be created according to CDISC standards (SDTM IG Version 3.2 & ADaM IG Version 1.1).
- For creation of ADaM datasets (ADC1/ADCM/ADAE), the same version of dictionary datasets will be implemented for conversion from SI to SDTM.

#### **Generation of RTF Files**

RTF files will be generated for all reporting efforts described in the RAP.

#### 10.3.2. Reporting Standards

#### General

- The current GSK Integrated Data Standards Library (IDSL) will be applied for reporting, unless otherwise stated (IDSL Standards Location: https://spope.gsk.com/sites/IDSLLibrary/SitePages/Home.aspx):
  - 4.03 to 4.23: General Principles
  - 5.01 to 5.08: Principles Related to Data Listings
  - 6.01 to 6.11: Principles Related to Summary Tables
  - 7.01 to 7.13: Principles Related to Graphics
- Do not include participant level listings in the main body of the GSK Clinical Study Report. All participant level listings should be located in the modular appendices as ICH or non-ICH listings.

#### **Formats**

- All data will be reported according to the actual treatment the participant received unless otherwise stated.
- GSK IDSL Statistical Principles (5.03 & 6.06.3) for decimal places (DP's) will be adopted for reporting of data based on the raw data collected, unless otherwise stated.
- Numeric data will be reported at the precision collected on the eCRF.
- The reported precision from non eCRF sources will follow the IDSL statistical principles but may be adjusted to a clinically interpretable number of DP's.

#### **Planned and Actual Time**

- Reporting for tables, figures, and formal statistical analyses:
  - Planned time relative to dosing will be used in figures, summaries, statistical analyses and calculation of any derived parameters, unless otherwise stated.
  - The impact of any major deviation from the planned assessment times and/or scheduled visit days on the analyses and interpretation of the results will be assessed as appropriate.
- Reporting for Data Listings:
  - Planned and actual time relative to study drug dosing will be shown in listings (Refer to IDSL Statistical Principle 5.05.1).
  - Unscheduled or unplanned readings will be presented within the participant's listings.

 Visits outside the protocol defined time-windows (i.e. recorded as protocol deviations) will be included in listings but omitted from figures (mean figures only for PK concentrations), summaries and statistical analyses (excluding statistical analyses of PK parameters).

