#### 4.1. Protocol Deviations

Important protocol deviations (including deviations related to study inclusion/exclusion criteria, conduct of the trial, participant management or participant assessment) will be summarised and listed.

Protocol deviations will be tracked by the study team throughout the conduct of the study in accordance with the Protocol Deviation Management Plan dated 11MAR2019. The "significant" protocol deviation in the Protocol Deviation Management Plan is equivalent to "important" protocol deviations.

- Data will be reviewed prior to freezing the database to ensure all significant deviations and deviations which may lead to exclusion from the analysis are captured and categorised on the protocol deviations dataset.
- This dataset will be the basis for the summaries and listings of protocol deviations.

A separate listing of all inclusion/exclusion criteria deviations will also be provided. This listing will be based on data as recorded on the inclusion/exclusion page of the electronic case record form (eCRF).

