### 5.2. Baseline Definitions

For all endpoints (except as noted in baseline definitions), the baseline value will be the latest pre-dose assessment with a non-missing value, including those from unscheduled visits. If time is not collected, Day 1 assessments are assumed to be taken prior to first dose and used as baseline. Baseline is applied to each treatment period.

Parameter	Study As	sessment Basel	s Considered as ine	Baseline Used in Data Display					
	Screening	Day -1	Day 1 (Pre-Dose)	Period 1 Period 2					
Safety									
Vital Sign	Х	Х	X	Day 1 (Pre-Dose) for each period					
12-Lead ECG	Х	Χ	Х	Day 1 (Pre-Dose)[1] for each period					
Hematology	Х	Х		Day -1 Period 1 Day 14					
Clinical Chemistry	Х	Х		Day -1 Period 1 Day 14					
Urinalysis	Х	Χ		Day -1	Period 1 Day 14				

 The average (for quantitative assessments) or the worst case (for interpretation) of the predose triplicate assessments on Day 1 of Period 1 will be used as the baseline for Period 1. The average (for quantitative assessments) or the worst case (for interpretation) of the predose triplicate assessments on Day 1 of Period 2 will be used as the baseline for Period 2.

Unless otherwise stated, if baseline data is missing no derivation will be performed and baseline will be set to missing.

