#### **Unscheduled Visits**

- Unscheduled visits will not be included in summary tables except for determining the worst-case values.
- Unscheduled visits will not be included in figures.
- All unscheduled visits will be included in listings.

Descriptive Summary Statistics					
Continuous Data	Refer to IDSL Statistical Principle 6.06.1				
Categorical Data	N, n, frequency, %				
Graphical Displays					
Refer to IDSL Statistical Principals 7.01 to 7.13.					

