## 10.4. Appendix 4: Derived and Transformed Data

#### 10.4.1. General

#### **Multiple Measurements at One Analysis Time Point**

- Mean of the measurements will be calculated and used in any derivation of summary statistics but if listed, all data will be presented.
- The worst finding/interpretation associated with multiple measurements as the finding/interpretation for that time point.
- Participants having both High and Low values for Normal Ranges at any post-baseline visit for safety parameters will be counted in both the High and Low categories of "Any visit post-baseline" row of related summary tables. This will also be applicable to relevant Potential Clinical Importance summary tables.

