#### **Period Day**

- Calculated as the number of days from First Dose Date for the respective period:
  - Assessment Date = Missing 
    → Study Day = Missing
  - Assessment Date < First Dose Date in Period 1 → Study Day = Assessment Date First Dose
    Date

  - First Dose Date in Period 1 <= Assessment Date < First Dose Date in Period 2 → Study Day =
     Assessment Date (First Dose Date in Period 1) + 1

  - Assessment Date >= First Dose Date in Period 2 → Study Day = Assessment Date (First Dose Date in Period 2) + 1

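### SAP 10.3.2 keeps out-of-window scheduled safety values out of the maximum-value tables, while equal unscheduled values count (minor)

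*SAP*

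**What the plan says.** The rule is in SAP 10.3.2, under Planned and Actual Time: "Visits outside the protocol defined time-windows (i.e. recorded as protocol deviations) will be included in listings but omitted from figures". The sentence continues: "mean figures only for PK concentrations), summaries and statistical analyses (excluding statistical analyses of PK parameters". Both exceptions in it concern PK. None concerns the worst value of a safety parameter.

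The next block of the same section, Unscheduled Visits, does contain such an exception: "Unscheduled visits will not be included in summary tables except for determining the worst-case values".

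Three other statements bear on the point:

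- SAP 10.3.2 also calls for an assessment, where appropriate, of the following: "The impact of any major deviation from the planned assessment times and/or scheduled visit days on the analyses and interpretation of the results".
- SAP 10.4.1 has a counting rule for normal ranges: "Participants having both High and Low values for Normal Ranges at any post-baseline visit for safety parameters will be counted in both", that is, once as high and once as low. It does not say whether out-of-window visits belong to that count.
- SAP 4.1 has deviations tracked "in accordance with the Protocol Deviation Management Plan dated 11MAR2019". That plan is not among the documents, and it governs what is recorded as a deviation.

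**The concern.** The plan deals with two kinds of observation that do not fit the schedule. For unscheduled visits it protects the worst case. For scheduled visits taken early or late it does not. The assessment the protocol asked for is therefore handled less conservatively than one it did not ask for, even if the two values are identical.

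The tables affected are those meant to show each participant's most extreme laboratory grade or QTc. Protocol 2.3 names QTc prolongation as one of three major risks of GSK3640254. About 16 participants are to be treated, so one participant in a lower category than the data support is visible in a table: 1/16 = 6.3%, or 1/12 = 8.3% if only the 12 evaluable participants remain.

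**Working it through.** **1. Which tables are touched.** SAP 10.9.1 numbers the safety tables 2.1 to 2.19, so there are 19. By title in SAP 10.9.5 they divide as follows:

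- 2.1 to 2.6, adverse events: 6
- 2.7 to 2.18, laboratory, ECG and vital signs: 12
- 2.19, C-SSRS listing: 1

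6 + 12 + 1 = 19, which agrees with the plan's numbering. Among the 12 visit-based tables, those reporting a maximum are 2.8 (chemistry), 2.10 (hematology) and 2.13 (urinalysis) for grade increase, and 2.16 and 2.17 for QTc. That is 5 tables: 5/19 = 26% of the safety tables and 5/12 = 42% of the visit-based ones. They are all of the maximum-grade laboratory tables and both maximum-QTc tables. Table 2.6 also uses a maximum, but of adverse event intensity, which is not a visit value.

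**2. Whether the omission reaches them.** All five are titled as summaries. The unscheduled-visit rule excludes such visits from summary tables and then needs an exception for worst-case values, so the SAP's own usage puts worst-case tables among the summaries. The sponsor's general reporting standards cannot supply the missing exception, because SAP 10.3.2 applies them only where nothing else is stated, and here something else is stated.

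**3. The two rules side by side, for the same abnormal post-baseline value.**

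| Source of the value | Listings | By-visit summaries | Maximum tables |
|---|---|---|---|
| Scheduled, in window | yes | yes | yes |
| Scheduled, recorded as out of window | yes | no | no |
| Unscheduled | yes | no | yes |

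The second and third rows differ only in the last column.

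**4. Direction.** Let S be the post-baseline values that count and x the omitted value. Then max(S) ≤ max(S ∪ {x}). For a given baseline b, max(S) − b is likewise no larger than it would be with x included. The reported maximum, or maximum increase, can only fall or stay the same.

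A hypothetical case: baseline grade 0, in-window post-baseline grades 0 and 1, out-of-window grade 2. The table reports a maximum increase of 1. Had the grade 2 value come from an unscheduled visit, it would report 2.

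**5. Frequency.** There is nothing to compute. The protocol's Schedule of Activities and Section 8.2 print no time windows for on-study laboratory, ECG or vital-sign assessments, and neither document gives a rate of timing deviations.

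**6. What other provisions catch.** Under Protocol 7.1.2, an on-treatment QTcF above 500 msec, or a rise above 60 msec, calls for two repeat unscheduled ECGs within 10 minutes. Those repeats count in Tables 2.16 and 2.17. Protocol 8.2.4 has clinically significant laboratory values repeated, and clinically relevant changes recorded as adverse events. Neither provision covers everything. A QTcF of, say, 470 msec with a rise of 40 msec triggers no repeat, although SAP 10.7.1 treats QTc above 450 msec as potentially clinically important.

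**The case against.** The best defence is that the rule may have little or nothing to act on. It applies only to visits outside protocol-defined windows that are recorded as deviations. No on-study safety windows are printed, and the plan that decides what is recorded is not available. Participants stay in the clinic from Day −1 to Period 2 Day 10 (Protocol 4.1). If the word visits means visit days, which is its more natural sense in that section, a missed day is improbable. Large QTcF changes and clinically significant laboratory values have other routes into the tables. Graded laboratory values and all ECG values stay in Listings 20 to 28, and the impact of major timing deviations is to be assessed. Finally, the count of five rests on titles; the table shells are not in the documents.

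Most of this stands as a limit on how often the point matters. It does not change what the rule says. Listings do not correct a count in a summary table, an impact assessment does not put the value back, and the repeat provisions leave smaller or unconfirmed changes uncovered.

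Two stronger readings are tempting and are not supported:

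- **Loss of baseline.** Because the Period 1 Day 14 laboratory panel is the Period 2 baseline, a reader might infer that a mistimed panel would also be lost as baseline. SAP 5.2 answers this: "the baseline value will be the latest pre-dose assessment with a non-missing value, including those from unscheduled visits". It sets no window condition, and the omission rule concerns figures, summaries and analyses, not eligibility as baseline.
- **Bias against one treatment column.** Period 2 has more ECG days than Period 1, so a reader might infer that losses would fall mainly on the combination. Both columns follow the same rule. Without windows or a deviation rate, the documents do not show that any value would be lost in either.

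**Conclusion.** The concern holds as a minor defect in the safety reporting rules. As written, an out-of-window scheduled laboratory or ECG value is left out of five of the 19 safety tables while an equal unscheduled value is counted, and the effect on a reported maximum is downward or nil. This rests on reading SAP 10.3.2 literally and on identifying the five tables by title.

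The frequency is unknown and probably low, and any numerical estimate would need a deviation rate that the documents do not give. No reported result is shown to change. Safety is a secondary objective with descriptive analysis only (Protocol 9.4.2), and the statistical analysis of PK parameters is expressly exempt from the omission, so the primary analysis is unaffected.

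**What to change.** Add one sentence to SAP 10.3.2, after the rule on out-of-window visits:

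> For safety data, out-of-window values are excluded from by-visit summaries and mean figures only; all post-baseline values, scheduled (in or out of window) and unscheduled, are used for maximum-grade, maximum-QTc and other worst-case summaries.

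This aligns the two rules and also settles how the any-visit row in SAP 10.4.1 is to be read. Section 5.2 needs no change. The amendment is free: no new data are needed, and by-visit summaries, mean figures and all PK analyses stay as planned. It should be made before the review of deviations that SAP 4.1 places ahead of the database freeze, so that the choice does not depend on which values turn out to be affected.

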#### **Unscheduled Visits**

- Unscheduled visits will not be included in summary tables except for determining the worst-case values.
- Unscheduled visits will not be included in figures.
- All unscheduled visits will be included in listings.

Descriptive Summary Statistics					
Continuous Data	Refer to IDSL Statistical Principle 6.06.1				
Categorical Data	N, n, frequency, %				
Graphical Displays					
Refer to IDSL Statistical Principals 7.01 to 7.13.					

## 10.3.3. Reporting Standards for Pharmacokinetics

Pharmacokinetic Con	centration Data
Descriptive Summary Statistics, Graphical Displays and Listings	Refer to IDSL PK Display Standards. Refer to IDSL Statistical Principle 6.06.1. For continuous data:  NQs at the beginning of a participant profile (i.e. before the first incidence of a measurable concentration) are deemed to be zero as it is assumed that in this circumstance no drug is yet measurable in the blood. For NQs at the end of the participant profile (i.e. after the last incidence of a measurable concentration); for individual plots and pharmacokinetic analyses these are dropped (set to missing) as they do not provide any useful information (and can erroneously indicate that absolutely no drug is present) for summary statistics, these are set to 0 (to avoid skewing of the summary statistics) Individual NQs which fall between two measurable concentrations are set to missing (individual values of this nature are assumed to be an anomaly) If two or more NQ values occur in succession between measurable concentrations, the profile will be deemed to have terminated at the last measurable concentration prior to these NQs. For the purpose of individual participant plots, these NQs will be set to 0, and the subsequent measurable concentrations will be retained. For the derivation of pharmacokinetic parameters, these NQs and any subsequent measurable concentrations will be omitted (set to missing).  Note: Concentration values will be imputed as per GUI_51487 for descriptive summary statistics/analysis and summarized graphical displays only.
Pharmacokinetic Para	
Descriptive Summary Statistics, Graphical Displays and Listings	N, n, geometric mean, 95% CI of geometric mean, SD of logged data and between subject geometric coefficient of variation (CVb (%)) will be reported. $ \text{CV}_b\left(\%\right) = \sqrt{\left(\text{exp}(\text{SD}^2) - 1\right) * 100} $ (SD = SD of Ln-Transformed data)
Parameters Not Being Ln- Transformed	Tmax, λz, λz lower, λz upper, and λz no. of points.

Parameters Not Being Summarized	λz, λz lower, λz upper, and λz no. of points.
Listings	Include the first point, last point and number of points used in the determination of λz and Rsq_adjusted for listings.

## 10.4. Appendix 4: Derived and Transformed Data

#### 10.4.1. General

#### **Multiple Measurements at One Analysis Time Point**

- Mean of the measurements will be calculated and used in any derivation of summary statistics but if listed, all data will be presented.
- The worst finding/interpretation associated with multiple measurements as the finding/interpretation for that time point.
- Participants having both High and Low values for Normal Ranges at any post-baseline visit for safety parameters will be counted in both the High and Low categories of "Any visit post-baseline" row of related summary tables. This will also be applicable to relevant Potential Clinical Importance summary tables.

### **Study Day**

- Calculated as the number of days from First Dose Date in Period 1:
  - Assessment Date = Missing → Study Day = Missing
  - Assessment Date < First Dose Date in Period 1 → Study Day = Assessment Date First Dose
    Date

  - Assessment Date >= First Dose Date in Period 1 → Study Day = Assessment Date (First Dose Date in Period 1) + 1

#### **Period Day**

- Calculated as the number of days from First Dose Date for the respective period:
  - Assessment Date = Missing 
    → Study Day = Missing
  - Assessment Date < First Dose Date in Period 1 → Study Day = Assessment Date First Dose
    Date

  - First Dose Date in Period 1 <= Assessment Date < First Dose Date in Period 2 → Study Day =
     Assessment Date (First Dose Date in Period 1) + 1

  - Assessment Date >= First Dose Date in Period 2 → Study Day = Assessment Date (First Dose Date in Period 2) + 1

## 10.4.2. Study Population

#### Age

- GSK standard IDSL algorithms will be used for calculating age where birth date will be imputed as follows:
  - Any participant with a missing day will have this imputed as day '15'.
  - Any participant with a missing day and month will have this imputed as PPD
- Birth date will be presented in listings as 'YYYY'.

#### **Body Mass Index (BMI)**

Calculated as Weight (kg) / [Height (m)]

## 10.4.3. Safety

## Adverse Events

## **AEs of Special Interest**

No analysis for AEs of Special Interest will be performed

## 10.5. Appendix 5: Reporting Standards for Missing Data

## 10.5.1. Premature Withdrawals

Element	Reporting Detail
General	
 
Participant study completion (i.e. as specified in the protocol) was defined as the participant has completed all phases of the study including the final date on which data were or are expected to be collected.
 
Withdrawn participants were not replaced in the study.
 
All available data from participants who were withdrawn from the study will be listed and all available planned data will be included in summary tables and figures, unless otherwise specified.
 

## 10.5.2. Handling of Missing Data

Element	Reporting Detail
General	Missing data occurs when any requested data is not provided, leading to blank fields on the collection instrument:
	
 
These data will be indicated by the use of a "blank" in participant listing displays.
 
Unless all data for a specific visit are missing in which case the data is excluded from the table.
 

	
 
Answers such as "Not applicable" and "Not evaluable" are not considered to be missing data and should be displayed as such.
 

Outliers	Any participants excluded from the summaries and/or statistical analyses will be documented along with the reason for exclusion in the clinical study report.

## 10.5.2.1. Handling of Missing and Partial Dates

Reporting Detail
Partial dates will be displayed as captured in participant listing displays.

 
The eCRF allows for the possibility of partial dates (i.e., only month and year) to be recorded for AE start and end dates; that is, the day of the month may be missing. In such a case, the following conventions will be applied for calculating the time to onset and the duration of the event:         
 
Missing Start Day: First of the month will be used unless this is before the start date of study treatment; in this case the study treatment start date will be used and hence the event is considered On-treatment as per Appendix 2: Study Phases and Treatment Emergent Adverse Events.
 
Missing Stop Day: Last day of the month will be used, unless this is after the stop date of study treatment; in this case the study treatment stop date will be used.
 
 
 

 
Completely missing start or end dates will remain missing, with no imputation applied.
 
Consequently, time to onset and duration of such events will be missing.
 

 
Partial dates for any concomitant medications recorded in the eCRF will be imputed using the following convention:
 
If the partial date is a start date, a '01' will be used for the day and 'Jan' will be used for the month
 
If the partial date is a stop date, a '28/29/30/31' will be used for the day (dependent on the month and year) and 'Dec' will be used for the month.
 
The recorded partial date will be displayed in listings.
 

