# 4. STUDY DESIGN

# 4.1. Overall Design

This is a Phase 1, open-label, fixed-sequence 2-period, one-way drug interaction study designed to assess the PK, safety, and tolerability of GSK3640254 and TAF/FTC when administered alone and in combination in healthy participants.

The study will consist of a screening period and 2 sequential treatment periods. Participants will be screened within 28 days before the first dose of study intervention. The treatments will be as follows:

- Treatment A: TAF/FTC 25/200 mg QD on Days 1 through 14 (Period 1)
- Treatment B: TAF/FTC 25/200 mg QD coadministered with GSK3640254 200 mg QD on Days 1 through 7 (Period 2)

There is no washout between the last dose of study intervention (Treatment A) in Period 1 and initiation of study intervention (Treatment B) in Period 2. The participants will fast overnight for at least 8 hours prior to dosing and will receive a moderate fat meal 30 minutes prior to dosing. Participants will eat this meal in 30 minutes or less. Dose administration will occur within 5 minutes of completion of meal consumption.

Pharmacokinetic blood samples for analysis of TAF, FTC, and TFV will be collected before dosing (0 hour) on Days 2 through 14 (Period 1) and Days 1 through 7 (Period 2) and up to 24 hours after TAF/FTC dosing on Period 1, Day 14 and Period 2, Day 7. Pharmacokinetic blood samples for analysis of GSK3640254 will be collected before dosing (0 hour) on Days 2 through 7 (Period 2) and up to 24 hours after GSK3640254 dosing on Day 7.

Safety and tolerability will be assessed by monitoring and recording of AEs, clinical laboratory test results, vital sign measurements, 12-lead ECG results, and physical examination findings.

Study assessments will be performed as indicated in the Schedule of Activities (SoA) (Section 1.3). Participants will be confined to the clinic from Day –1 until discharge on Period 2, Day 10.

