# 8.3.1. Time Period and Frequency for Collecting AE and SAE Information

- All SAEs will be collected from the signing of the ICF until the end of the study at the time points specified in the SoA (Section 1.3).
- All AEs will be collected from the start of intervention until the end of the study at the time points specified in the SoA (Section 1.3).
- Medical occurrences that begin before the start of study intervention but after obtaining informed consent will be recorded on the Medical History/Current Medical Conditions section of the CRF, not the AE section.
- All SAEs will be recorded and reported to the sponsor or designee immediately and under no circumstance should this exceed 24 hours, as indicated in Appendix 6. The investigator will submit any updated SAE data to the sponsor within 24 hours of it being available.
- Investigators are not obligated to actively seek AEs or SAEs after the conclusion of the study participation. However, if the investigator learns of any SAE, including a death, at any time after a participant has been discharged from the study, and he/she considers the event to be reasonably related to the study intervention or study participation, the investigator must promptly notify the sponsor.

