# 8.3.3. Follow-up of AEs and SAEs

After the initial AE/SAE report, the investigator is required to proactively follow each participant at subsequent visits/contacts. All SAEs will be followed until the event is resolved, stabilized, otherwise explained, or the participant is lost to follow-up (as defined in Section 7.3). Further information on follow-up procedures is given in Appendix 6.

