## 10.2.2. Treatment Emergent Flag for Adverse Events

Flag	Definition
Treatment Emergent	
 
If AE onset date and time is on or after treatment start date and time & on or before treatment stop date and time + 4 days.
 
Study Treatment Start Date and Time ≤ AE Start Date and Time ≤ Study Treatment Stop Date and Time + 4 days.
 
If the AE onset date is completely missing, the AE is considered as treatment emergent.
 

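### The SAP caps a partial AE stop date (day missing) at the last dose, so the calculated duration is negative for known follow-up onsets and cut short for AEs that outlast dosing

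*SAP*

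**What the plan says.** SAP 10.5.2.1 deals with AE dates recorded as month and year only, and states the purpose: "the following conventions will be applied for calculating the time to onset and the duration of the event".

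- Start day missing: "Missing Start Day: First of the month will be used unless this is before the start date of study treatment", in which case treatment start is used.
- Stop day missing: "Missing Stop Day: Last day of the month will be used, unless this is after the stop date of study treatment". If month-end is later than the last dose, the imputed stop becomes the last dose date.

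The same section leaves completely missing dates missing and shows partial dates in listings as they were captured.

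Other sections let AEs start or continue after the last dose:

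- Protocol 8.3.1: "All AEs will be collected from the start of intervention until the end of the study". Protocol 4.1 puts discharge at Period 2 Day 10.
- SAP 10.2.2 defines treatment-emergent as "Study Treatment Start Date and Time ≤ AE Start Date and Time ≤ Study Treatment Stop Date and Time + 4 days".
- Protocol 8.3.3: "All SAEs will be followed until the event is resolved, stabilized, otherwise explained, or the participant is lost to follow-up". Protocol 8.3 adds follow-up of AEs that are related or that caused discontinuation.

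**The concern.** The start-day rule has a sensible bound: an imputed onset cannot precede treatment. The stop-day rule lacks the matching one, that a stop cannot precede onset, and uses the last dose as its upper limit instead. The last dose is not the end of AE observation in this study. The SAP accepts AEs that begin in the days after dosing, then assigns those with a missing stop day a stop at the last dose.

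What is at stake is the calculated duration of such events. The error runs one way: an event that outlasts dosing is shortened, never lengthened. The exposed records are those the protocol follows past dosing, including safety withdrawals (Protocol 7.2) and raised ALT monitored until it resolves or stabilises (Protocol Appendix 5). The concomitant-medication rule in the same SAP section imputes partial stop dates with no cap at treatment stop.

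**Working it through.** The plan gives no figure to reproduce, so the check applies the rule as written.

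**Inputs**
- Last dose L = Period 2 Day 7. Protocol 4.1 has 14 days, no washout, then 7 days: study day 14 + 7 = 21.
- Discharge = Period 2 Day 10 = study day 14 + 10 = 24.
- Treatment-emergent window: to L + 4 days (SAP 10.2.2), which covers Days 8 to 10.
- Rule: let M be the last day of the recorded stop month. Imputed stop = L if M > L, otherwise M.

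**1. When the cap applies.** Let S be the true stop. M is never earlier than S. If S > L, then M ≥ S > L, so the imputed stop is always L.

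**2. Known onset after the last dose.** Imputed stop minus onset:
- Day 8: 7 − 8 = −1 day
- Day 9: 7 − 9 = −2 days
- Day 10: 7 − 10 = −3 days

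**3. Onset on treatment, true stop after the last dose.** Take an assumed first dose of 1 April, so last dose is 21 April and discharge 24 April. For onset on Period 2 Day 5 (19 April) and true stop 24 April, the true duration is 24 − 19 + 1 = 6 days. If only April is recorded for the stop, month-end is 30 April, later than 21 April, so the imputed stop is 21 April and the duration is 21 − 19 + 1 = 3 days.

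**4. Imputed stop in a different month.** With an assumed first dose of 10 April, last dose is 30 April. An AE that stopped on Day 8 (1 May), recorded as May, is imputed as 30 April.

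**5. Enumeration.** The rule was applied to all 365 first-dose dates of an assumed non-leap year, with every onset and stop day pair weighted equally.

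| Situation (stop day missing) | Pairs | Result |
|---|---|---|
| Known onset Days 8–10, stop by Day 10 | 365 × 6 = 2190 | Stop before onset in 2190 (100%) |
| As above, onset day also missing | 2190 | Stop before imputed onset in 120 (120/2190 = 5.5%) |
| Onset on treatment, true stop Days 8–10 | 365 × 21 × 3 = 22,995 | Cut to last dose in 22,995 (100%); different month in 1512 (1512/22,995 = 6.6%) |
| True stop on or before last dose | 365 × 231 = 84,315 | Ended early in 0 |

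The 120 cases arise when onset falls in a month after that of the last dose. Otherwise the start-day rule moves onset back to a date no later than the last dose. These counts show how the rule behaves, not how often partial dates will occur.

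**6. After a fix.** With the cap moved to Day 10 for stops within the study and a floor at onset, 0 of 2190 stops precede onset and 0 of 22,995 events end before their true stop.

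**The case against.** The strongest case on the other side is that the rule will hardly ever operate and that nothing reported depends on it. Most of this stands.

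- **Scope.** A reader might infer that every AE outlasting treatment is ended at the last dose. The documents do not support that. Only records with month and year but no day are affected; an AE with no end date stays without one.
- **Recorded data.** A reader might infer that such events are recorded as resolved on the last dosing day. They are not. Listings show the partial date as captured, and the imputed date is used only for time to onset and duration.
- **Outputs.** SAP Tables 2.1 to 2.6 cover incidence, relatedness, seriousness and maximum intensity. None has duration as its subject. A duration column might appear in an AE listing, but the shells are not in the documents, so this cannot be confirmed. Treatment-emergent status depends on onset.
- **Causality.** It is tempting to say the rule makes events seem to resolve when dosing stops, and so suggests a drug effect. That is speculative: under Protocol Appendix 6 the investigator judges causality on clinical grounds, not from an imputed date.
- **Follow-up.** Follow-up past discharge is required for serious, related or discontinuation AEs, not for all AEs.
- **Frequency.** Participants are confined to Day 10, so partial dates within the study should be rare. Partial stops may be likelier after discharge, but the documents give no frequency.

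None of this makes the rule right where it does apply. No other part of the SAP adds a floor at onset or an exception for events after the last dose.

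**Conclusion.** The rule is wrong as written, with a small effect. For an AE with a known onset on Period 2 Days 8 to 10 and a missing stop day, it always gives a stop 1 to 3 days before onset. For any AE with a missing stop day that outlasted dosing, it always cuts the calculated duration at the last dose. The effect is confined to calculated AE duration. AE incidence, treatment-emergent classification, the planned AE tables and the PK analyses do not change, and few records are expected among about 16 participants.

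This rests on two assumptions. First, the treatment stop date is read as the final dose in Period 2; a per-period reading would move the cap earlier for Period 1 events. Second, the 1-to-3-day figure assumes dosing to Day 7. For a participant who stops early, the cap moves to the earlier last dose and the gap can exceed 3 days.

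**What to change.** In SAP 10.5.2.1, remove the cap at treatment stop from the stop-day rule. Impute a missing AE stop day as the earlier of month-end and the participant's last study contact (or the data cut for events followed after discharge), and never before the AE onset date.

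The cost is one sentence in the SAP and one line of derivation code, with no effect on data collection. There is one small trade-off. An AE that truly ended during dosing, with its stop day missing, may be imputed somewhat later than under the present rule: by at most 10 − 7 = 3 days for a participant dosed to Day 7 whose last contact is Day 10.
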